8.3 Reasons for Removal From Treatment or Study

8.3.1 Reasons for Removal From Treatment

Reasons for removal from protocol-required investigational product(s) or procedural assessments include any of the following:

- subject request
- safety concern (eg, due to an adverse event, ineligibility determined, protocol deviation, non-compliance, requirement for alternative therapy, protocol-specified criteria [see [Section 6.2.1.2](#)], pregnancy)
- death
- lost to follow-up
- decision by Sponsor (other than subject request, safety concern, lost to follow-up)

8.3.2 Reasons for Removal From Study

Reasons for removal of a subject from the study are:

- decision by sponsor
- withdrawal of consent from study
- death
- lost to follow-up

Approved

8.4 Lost to Follow-up

A subject will be considered lost to follow-up at the end of the study if he or she repeatedly fails to return for scheduled visits and is unable to be contacted by the study site.

The site must attempt to contact the subject at each scheduled visit and reschedule the missed visit as soon as possible and counsel the subject on the importance of maintaining the assigned visit schedule and ascertain whether or not the subject wishes to and/or is able to continue in the study. These contact attempts are to be documented in the subject's medical record.

For subjects who are lost to follow-up, the investigator (or vendors approved by the site) can search publicly available records as permitted by applicable law to ascertain survival status. This ensures that the data set(s) produced as an outcome of the study is/are as comprehensive as possible.

9. SAFETY DATA COLLECTION, RECORDING, AND REPORTING

9.1 Definition of Safety Events

9.1.1 Disease-related Events

Disease-related events are events (serious or non-serious) anticipated to occur in the study population due to the underlying disease. In this study, subjects have hyperlipidemia and clinically evident atherosclerotic CVD. Therefore, disease-related events include the following: manifestations and complications of atherosclerotic vascular disease such as coronary artery disease, angina, MI, ischemic stroke, TIA, carotid artery disease, peripheral vascular disease (including complications such as claudication), and testing suggesting progression of atherosclerotic vascular disease. Such events do not meet the definition of an adverse event unless assessed to be more severe than expected for the subject's condition.

Disease-related events that do not qualify as adverse events or serious adverse events:

- An event which is part of the normal course of disease under study (eg, disease progression in oncology or hospitalization due to disease progression) is to be reported as a disease-related event.
- Death due to the disease under study is to be recorded on the Event eCRF.

Approved

Disease-related events that would qualify as an adverse event or serious adverse event:

- An event based on the underlying disease that is worse than expected as assessed by the investigator for the subject's condition or if the investigator believes there is a causal relationship between the investigational product (evolocumab)/study treatment/protocol-required therapies and disease worsening, this must be reported as an adverse event or serious adverse event.

Disease-related events will be collected through OLE duration including the safety follow-up visit, and will be **recorded** using the Event eCRF per [Section 9.2.1](#).

9.1.2 Adverse Events

An adverse event is defined as any untoward medical occurrence in a clinical trial subject. The event does not necessarily have a causal relationship with study treatment. The investigator is responsible for ensuring that any adverse events observed by the investigator or reported by the subject are recorded in the subject's medical record.

The definition of adverse events includes worsening of a pre-existing medical condition. Worsening indicates that the pre-existing medical condition or underlying disease (eg, diabetes, migraine headaches, gout) has increased in severity, frequency, and/or duration more than would be expected, and/or has an association with a significantly worse outcome than expected. A pre-existing condition that has not worsened more than anticipated (ie, more than usual fluctuation of disease) during the study or involves an intervention such as elective cosmetic surgery or a medical procedure while on study, is not considered an adverse event.

An adverse device effect is any adverse event related to the use of a medical device. Adverse device effects include adverse events resulting from insufficient or inadequate instructions for use, adverse events resulting from any malfunction of the device, or adverse events resulting from use error or from intentional misuse of the device.

The investigator's clinical judgment is used to determine whether a subject is to be removed from treatment due to an adverse event. In the event a subject, or subject's legally acceptable representative requests to withdraw from protocol-required therapies or the study due to an adverse event, refer to [Section 8.1](#) for additional instructions on the procedures recommended for safe withdrawal from protocol-required therapies or the study.

Approved

9.1.3 Serious Adverse Events

A serious adverse event is defined as an adverse event that meets at least 1 of the following serious criteria (unless it meets the definition of a disease-related event as defined in [Section 9.1.1](#)):

- fatal
- life threatening (places the subject at immediate risk of death)
- requires in-patient hospitalization or prolongation of existing hospitalization
- results in persistent or significant disability/incapacity
- congenital anomaly/birth defect
- other medically important serious event

A disease-related event (eg, angina) is to be reported as a serious adverse event if:

- the subject's pre-existing condition becomes worse than what the investigator would consider typical for a patient with the same underlying condition, or
- if the investigator believes a causal relationship exists between the investigational medicinal product(s)/protocol-required therapies and the event,
- and the event meets at least 1 of the serious criteria.

An adverse event would meet the criterion of "requires hospitalization", if the event necessitated an admission to a health care facility (eg, overnight stay).

If an investigator considers an event to be clinically important, but it does not meet any of the serious criteria, the event could be classified as a serious adverse event under the criterion of "other medically important serious event". Examples of such events could include allergic bronchospasm, convulsions, blood dyscrasias, DILI (see [Appendix A](#) for DILI reporting criteria), or events that necessitate an emergency room visit, outpatient surgery, or urgent intervention.

9.2 Safety Event Reporting Procedures

9.2.1 Reporting Procedures for Disease-Related Events

The investigator is responsible for ensuring that all disease-related events observed by the investigator or reported by the subject that occur after signing the ICF through the EOS/Safety Follow-Up visit for this study, or 30 days (+ 3 days) after the last administration of evolocumab, whichever is later, are recorded on the Event eCRF as a disease-related event.

All serious disease-related events will be recorded and reported to the sponsor or designee within 24 hours. The investigator will submit any updated serious disease-related event data to the sponsor within 24 hours of it being available.

Disease-related events assessed by the investigator to be more severe than expected and/or related to the investigational medicinal product (evolocumab)/study treatment/protocol-required therapies, and determined to be serious, must be recorded on the Event eCRF as serious adverse events.

Additionally, the investigator is required to report a fatal disease-related event on the Event eCRF as a disease-related event.

9.2.2 Adverse Events

9.2.2.1 Reporting Procedures for Adverse Events That do not Meet Serious Criteria

The investigator is responsible for ensuring that all adverse events and adverse device effects observed by the investigator or reported by the subject that occur after signing the ICF through the EOS/Safety Follow-Up visit for this OLE study, or 30 days (+ 3 days) after the last administration of evolocumab, whichever is later, are reported using the Event eCRF.

The investigator must assign the following adverse event attributes:

- adverse event diagnosis or syndrome(s), if known (if not known, signs or symptoms)
- dates of onset and resolution (if resolved)
- severity
- assessment of relatedness to investigational product (evolocumab and/or the medical devices [prefilled AI/pen or PI]), any study-mandated activity or procedure, or other protocol-required/study-mandated therapies)
- action taken

If the severity of an adverse event changes from the date of onset to the date of resolution, record as a single event with the worst severity on the Event eCRF.

The adverse event grading scale used will be the Common Terminology Criteria for Adverse Events (CTCAE). The grading scale used in this study is described in [Appendix A](#).

The investigator must assess whether the adverse event is possibly related to investigational medicinal product (evolocumab) and/or other protocol-required therapies. This relationship is indicated by a “yes” or “no” response to the question: Is there a reasonable possibility that the event may have been caused by the investigational medicinal product and/or other protocol-required therapies?

The investigator must assess whether the adverse event is possibly related to the prefilled AI/Pen or PI investigational devices used to administer investigational medicinal

Approved

product (evolocumab). The relationship is indicated by a “yes” or “no” response to the question: Is there a reasonable possibility that the event may have been caused by the investigational device?

The investigator must assess whether the adverse event is possibly related to any study-mandated activity (eg, administration of investigational product, protocol-required therapies, use of medical devices and/or procedure including any screening procedures). This relationship is indicated by a “yes” or “no” response to the question: Is there a reasonable possibility that the event may have been caused by a study activity (eg, administration of investigational product, protocol-required therapies, use of medical devices), and/or procedure?

The investigator is responsible for reviewing laboratory test results and determining whether an abnormal value in an individual study subject represents a clinically significant change from the subject’s baseline values. In general, abnormal laboratory findings without clinical significance (based on the investigator’s judgment) are not to be recorded as adverse events. However, laboratory value changes that require treatment or adjustment in current therapy are considered adverse events. Where applicable, clinical sequelae (not the laboratory abnormality) are to be recorded as the adverse event.

The investigator is expected to follow reported adverse events until stabilization or reversibility.

9.2.2.2 Reporting Procedures for Serious Adverse Events

The investigator is responsible for ensuring that all serious adverse events observed by the investigator or reported by the subject that occur after signing the ICF through the EOS/Safety Follow-Up visit for this study, or 30 days (+ 3 days) after the last administration of evolocumab, whichever is later are recorded in the subject’s medical record and are submitted to Amgen. All serious adverse events must be submitted to Amgen within 24 hours following the investigator’s knowledge of the event via the Event eCRF.

If the electronic data capture (EDC) system is unavailable to the site staff to report the serious adverse event, the information is to be reported to Amgen via an electronic Serious Adverse Event (eSAE) Contingency Report Form within 24 hours of the investigator’s knowledge of the event. See [Appendix B](#) for a sample of the Serious Adverse Event Worksheet/eSAE Contingency Report Form. For EDC studies where the

first notification of a Serious Adverse Event is reported to Amgen via the eSAE Contingency Report Form, the data must be entered into the EDC system when the system is again available.

The investigator must assess whether the serious adverse event is possibly related to investigational medicinal product (evolocumab) and/or other protocol-required therapies. This relationship is indicated by a “yes” or “no” response to the question: Is there a reasonable possibility that the event may have been caused by the investigational medicinal product and/or other protocol-required therapies?

The investigator must assess whether the serious adverse event is possibly related to the prefilled AI/Pen or PI investigational devices used to administer investigational medicinal product (evolocumab). The relationship is indicated by a “yes” or “no” response to the question: Is there a reasonable possibility that the event may have been caused by the investigational device?

The investigator must assess whether the serious adverse event is possibly related to any study-mandated activity (eg, administration of investigational product, protocol-required therapies, use of medical devices and/or procedure including any screening procedures). This relationship is indicated by a “yes” or “no” response to the question: Is there a reasonable possibility that the event may have been caused by a study activity (eg, administration of investigational product, protocol-required therapies, use of medical devices), and/or procedure?

The investigator is expected to follow reported serious adverse events until stabilization or reversibility.

New information relating to a previously reported serious adverse event must be submitted to Amgen. All new information for serious adverse events must be sent to Amgen within 24 hours following knowledge of the new information. If specifically requested, the investigator may need to provide additional follow-up information, such as discharge summaries, medical records, or extracts from the medical records. Information provided about the serious adverse event must be consistent with that recorded on the Event eCRF.

If a subject is permanently withdrawn from protocol-required therapies because of a serious adverse event, this information must be submitted to Amgen.

Amgen will report serious adverse events and/or suspected unexpected serious adverse reactions as required to regulatory authorities, investigators/institutions, and IRBs/IECs

in compliance with all reporting requirements according to local regulations and good clinical practice (GCP).

The investigator is to notify the appropriate IRB/IEC of serious adverse events occurring at the site and other adverse event reports received from Amgen, in accordance with local regulatory requirements and procedures.

9.2.2.3 Reporting Serious Adverse Events After the Protocol-required Reporting Period

There is no requirement to monitor study subjects for serious adverse events following the protocol-required reporting period or after EOS. However, these serious adverse events can be reported to Amgen. In some countries (eg, European Union [EU] member states), investigators are required to report serious adverse events that they become aware of after end of study. If serious adverse events are reported, the investigator is to report them to Amgen within 24 hours following the investigator's knowledge of the event.

Serious adverse events reported outside of the protocol-required reporting period will be captured within the safety database as clinical trial cases for the purposes of expedited reporting.

9.3 Pregnancy and Lactation Reporting

If a female subject becomes pregnant while the subject is taking evolocumab report the pregnancy to Amgen Global Patient Safety as specified below.

In addition to reporting any pregnancies occurring during the study, investigators should report pregnancies that occur for an additional 15 weeks after the last dose of evolocumab.

The pregnancy should be reported to Amgen Global Patient Safety within 24 hours of the investigator's knowledge of the event of a pregnancy. Report a pregnancy on the Pregnancy Notification Worksheet ([Appendix C](#)). Amgen Global Patient Safety will follow-up with the investigator regarding additional information that may be requested.

If a female subject becomes pregnant during the study, the investigator should attempt to obtain information regarding the birth outcome and health of the infant.

If the outcome of the pregnancy meets a criterion for immediate classification as a serious adverse event (eg, female subject experiences a spontaneous abortion, stillbirth, or neonatal death or there is a fetal or neonatal congenital anomaly) the investigator will report the event as a serious adverse event.

If a female breastfeeds while taking protocol-required therapies report the lactation case to Amgen as specified below.

Any lactation case should be reported to Amgen Global Patient Safety within 24 hours of the investigator's knowledge of event. Report a lactation case on the Lactation Notification Worksheet ([Appendix C](#)). Amgen Global Patient Safety will follow-up with the investigator regarding additional information that may be requested.

If a male subject's female partner becomes pregnant, the investigator should discuss obtaining information regarding the birth outcome and health of the infant from the pregnant partner.

Amgen is sponsoring a prospective, observational study of pregnant women who have been exposed to Repatha® (evolocumab) at any point during pregnancy and/or breastfeeding. The registry is conducted in Europe, South Africa, and Australia.

Participants are not asked to make any changes to their healthcare routine. While subjects who are pregnant are not eligible for the 20160250 study, if a site investigator/health care practitioner has a subject who becomes pregnant while receiving evolocumab, they will be advised to refer the subject to Amgen's evolocumab pregnancy registry according to the place of residency. More information on the pregnancy registry study in Europe, South Africa, and Australia is available in the respective study protocol (Protocol ID: 20150162 and the following websites; ClinicalTrials.gov and AmgenTrials.com.

10. STATISTICAL CONSIDERATIONS

10.1 Study Endpoints, Analysis Sets, and Covariates

10.1.1 Study Endpoints

10.1.1.1 Primary Endpoint

The primary endpoint is the subject incidence of adverse events.

10.1.1.2 Secondary Endpoints

The secondary endpoints for this study are the following:

- percent change of LDL-C from baseline at each scheduled visit
- achievement of an LDL-C < 40 mg/dL (1.03 mmol/L) at each scheduled visit

10.1.1.3 Exploratory Endpoints

The exploratory endpoints for this study are the following:

- Change and percent change from baseline at each scheduled visit in each of the following lipid parameters:
 - total cholesterol
 - triglycerides
 - HDL-C
 - VLDL-C
 - LDL-C
 - non-HDL-C
 - ApoA1
 - ApoB
 - Lp(a)
- Subject incidence of events positively reviewed by the CEC:
 - All deaths
 - Cardiovascular events of interest:
 - MI
 - Stroke
 - **Coronary** revascularization
 - Hospitalization for unstable angina
 - Hospitalization for heart failure
 - TIA

10.1.2 Analysis Sets

The OLE safety analysis set includes all subjects who received at least 1 dose of open-label evolocumab in the OLE study. This analysis set will be used for all analyses.

10.1.3 Covariates and Subgroups

The planned covariates and subgroups include the following:

- age (< 65 years, ≥ 65 years)
- sex (male, female)
- race

10.1.4 Handling of Missing and Incomplete Data

No missing value imputation is planned for primary, secondary, or exploratory endpoints.

Approved

10.2 Sample Size Considerations

It is estimated approximately 1600 subjects who completed the FOURIER trial will be enrolled. Based on sample size of 1600 subjects, [Table 5](#) lists the width of 95% confidence interval (CI) for a range of various underlying adverse event rates.

Table 5. Confidence Interval Width for Adverse Event Rates

Underlying Adverse Event Rate (%)	Width of 95% Confidence Interval
0.01	0.098
0.05	0.219
0.10	0.310
1.00	0.975
2.00	1.372
3.00	1.672
4.00	1.920
5.00	2.136

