10.4 Planned Methods of Analysis

10.4.1 General Considerations

Statistical analyses in this open label study are descriptive in nature. No statistical inference or missing value imputation is planned. No formal hypothesis will be tested in this study. Subject disposition, demographics, and baseline characteristics will be summarized. Summary statistics for continuous variables will include the number of subjects, mean, median, standard deviation or standard error, minimum, and maximum. For categorical variables, the frequency and percentage will be given. Unless specified otherwise, the baseline value is defined as the subject's baseline value from the parent study (FOURIER) and all analyses (primary, secondary, exploratory, and safety) will be performed on the OLE safety analysis set. For all endpoints, results will be summarized

by the randomized treatment group from the FOURIER study and overall, unless specified otherwise.

The primary analysis of all primary, secondary, and exploratory endpoints will use data from the OLE study only. Additional analyses combining the data from the OLE study and FOURIER study will be performed as applicable.

All deaths and cardiovascular events of interest (MI, stroke, **coronary** revascularization, hospitalization for unstable angina, hospitalization for heart failure, and TIA) will be reviewed by an independent external CEC, using standardized definitions. The CEC is external to Amgen and primarily comprises both academic clinical physicians (to include cardiologists) and medical reviewers trained on the clinical trial protocol, the CEC charter, and CEC processes. The chairman of the CEC is responsible for overseeing the operations in conformance with the CEC charter and for supervising the flow of data between the sponsor/data management and the CEC. Committee members are qualified in the appropriate subspecialty and free of conflict of interest. The CEC reviews events according to pre-specified criteria defined in the CEC charter. The CEC will be blinded to the original randomized treatment group from the FOURIER study.

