3.2 Sample Size

It is estimated approximately 1600 subjects who completed the FOURIER trial will be enrolled. Based on sample size of 1600 subjects, [Table 3-1](#) lists the width of 95% confidence interval (CI) for a range of various underlying adverse event rates.

Table 3-1. Confidence Interval Width for Adverse Event Rates

Underlying Adverse Event Rate (%)	Width of 95% Confidence Interval
0.01	0.098
0.05	0.219
0.10	0.310
1.00	0.975
2.00	1.372
3.00	1.672
4.00	1.920
5.00	2.136

4. Covariates and Subgroups

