9.1 General Considerations

Statistical analyses in this open-label study are descriptive in nature. No formal hypothesis will be tested in this study. No statistical inference is planned.

Subject disposition, demographics, and baseline characteristics and exposure to IP will be summarized.

Summary statistics for continuous variables will include the number of subjects (n), mean, standard deviation (SD) or standard error (SE), median, the first (Q1) and third (Q3) quartiles, minimum, and maximum. For categorical variables, the frequency and percentage will be given. The baseline value is defined as the subject's baseline value from the **parent** study as defined in [Section 5.2](#), unless specified otherwise. All analyses will be performed on the OLE safety analysis set.

Interim and final analyses will be based on data collected from this study combined with the data from the FOURIER study as applicable. For all endpoints, results will be summarized by the randomized treatment group from the parent study and overall, unless specified otherwise.

All deaths and cardiovascular events of interest (MI, stroke, coronary revascularization, hospitalization for unstable angina, hospitalization for heart failure, and TIA) will be reviewed by an independent external CEC, using standardized definitions. The CEC is external to Amgen and primarily comprises both academic clinical physicians (to include cardiologists) and medical reviewers trained on the clinical trial protocol, the CEC charter, and CEC processes. The chairman of the CEC is responsible for overseeing the operations in conformance with the CEC charter and for supervising the flow of data between the sponsor/data management and the CEC. Committee members are qualified in the appropriate subspecialty and free of conflict of interest. The CEC reviews events according to pre-specified criteria defined in the CEC charter. The CEC will be blinded to the original randomized treatment group from the **parent** study.

There will be no imputation for missing data other than date imputation described in [Section 8.3.2](#)

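### The only sample-size support is a table of normal-approximation interval widths that does not hold for adverse event rates of 0.01% to 0.10%

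*Protocol*

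**What the plan says.** Protocol 10.2 bases the number of subjects on expected roll-over from the parent trial: "It is estimated approximately 1600 subjects who completed the FOURIER trial will be enrolled". It then offers one quantitative statement, Table 5, which for that number of subjects "lists the width of 95% confidence interval (CI) for a range of various underlying adverse event rates". The table has a column headed "Underlying Adverse Event Rate", in percent, and a column of widths. The rates are 0.01, 0.05, 0.10, 1, 2, 3, 4 and 5%, and the widths are 0.098, 0.219, 0.310, 0.975, 1.372, 1.672, 1.920 and 2.136. SAP 3.2 repeats the same figures in Table 3-1, "Confidence Interval Width for Adverse Event Rates".

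Neither document names the interval method, shows limits or comments on small counts. The study is descriptive: Protocol 10.4.1 states "No formal hypothesis will be tested in this study" and SAP 9.1 states "No statistical inference is planned". The adverse event analyses (Protocol 10.4.2, SAP 9.5.1) specify no confidence interval.

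**The concern.** With no hypothesis test and no power calculation, the stated precision is the whole statistical argument for what 1600 subjects can show. The first three rows concern events rarer than 1 in 900, and at such rates very few subjects, often none, will have the event. A width taken from the normal approximation then describes no interval that could be computed from the data.

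This matters because the primary objective is long-term safety (Protocol 1.1), and Protocol 10.3.1 ties early stopping to a major unexpected safety signal. A reader who asks what the study can rule out will look at the rare-event rows. The 0.01% row suggests that an event affecting 1 subject in 10,000 would be estimated with an interval about 0.1 percentage point wide. The design does not have that property.

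**Working it through.** **Inputs.** n = 1600, the rates and the widths come from Protocol 10.2, Table 5 (identical in SAP Table 3-1). The level is 95%, taken as two-sided because a width is given (z = 1.96). The number of subjects with an event is treated as binomial(1600, p).

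**Step 1: reproduce the stated widths.** The Wald width is 2 × z × √(p(1 − p)/n). For p = 0.0001 this is 3.92 × √(0.0001 × 0.9999/1600) = 3.92 × 0.00025 = 0.00098, or 0.098 percentage points. All eight rows match to three decimals. Exact and Wilson widths do not match.

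**Step 2: lower limits.** The Wald lower limit is negative whenever p < z²/(n + z²) = 3.84/1603.84 = 0.24%. The first three rows fall below this value and the other five lie above it.

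**Step 3: probability of no event, and coverage.** P(no event) = (1 − p)^1600. With no event, the Wald interval has zero width and misses the true rate. Coverage is the sum of binomial probabilities over the counts whose Wald interval contains p.

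**Step 4: exact and Wilson widths.** The expected Clopper-Pearson width averages the exact width over the binomial distribution. The Wilson width is evaluated at the nominal rate.

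| Rate (%) | Stated width | Wald width | Wald lower limit (%) | Expected subjects with event | Wald coverage (%) | Expected exact width | Exact ÷ stated | Wilson width |
|---|---|---|---|---|---|---|---|---|
| 0.01 | 0.098 | 0.0980 | −0.039 | 0.16 | 14.79 | 0.2485 | 2.54 | 0.2587 |
| 0.05 | 0.219 | 0.2191 | −0.060 | 0.8 | 55.06 | 0.3153 | 1.44 | 0.3242 |
| 0.10 | 0.310 | 0.3097 | −0.055 | 1.6 | 79.69 | 0.3876 | 1.25 | 0.3910 |
| 1 | 0.975 | 0.9751 | 0.51 | 16 | 94.47 | 1.0386 | 1.07 | 1.0018 |
| 2 | 1.372 | 1.3720 | 1.31 | 32 | 94.45 | 1.4344 | 1.05 | 1.3895 |
| 3 | 1.672 | 1.6717 | 2.16 | 48 | 94.42 | 1.7335 | 1.04 | 1.6848 |
| 4 | 1.920 | 1.9204 | 3.04 | 64 | 94.60 | 1.9817 | 1.03 | 1.9307 |
| 5 | 2.136 | 2.1358 | 3.93 | 80 | 94.63 | 2.1968 | 1.03 | 2.1441 |

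P(no event) is 85.2%, 44.9% and 20.2% in the first three rows. From 1% upward it is effectively zero.

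**Step 5: which widths can occur.** With 0 events in 1600 the exact two-sided 95% interval runs from 0 to 1 − 0.025^(1/1600) = 0.230%. With 1 event it runs from 0.0016% to 0.3477%, a width of 0.346. At these low counts the narrowest exact width is therefore 0.230. The stated 0.098 and 0.219 are below it, and 0.310 falls between the two possible values. The Wald formula applied to data does not give these widths either: 0 events gives 0, 1 event gives 3.92 × √((1/1600)(1599/1600)/1600) = 0.245, and 2 events give 0.346.

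**Step 6: what zero events would show.** The two-sided upper limit of 0.230% is 1 in 434. The one-sided 95% limit is 1 − 0.05^(1/1600) = 0.187%, close to 3/1600 = 0.1875%.

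**The case against.** The strongest reply is that nothing depends on the table. N follows from how many parent-trial completers are expected to enrol. There is no precision target, no test and no planned interval for adverse events. Every printed figure is correct for a standard formula. The rows at 1% to 5% are sound, and SAP 9.5.1 uses a 1% threshold for its frequency-ordered summary. This stands, and it limits the consequence: no analysis or conclusion would change.

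A second reply is that the table gives widths at an assumed rate, while coverage and zero-width intervals belong to an interval computed from data, which the plan does not specify. The negative limits are also not printed. The distinction is fair, but the documents label the figures as widths of a 95% confidence interval. In the three rare rows no interval from 1600 subjects, exact or Wald, has the stated width.

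A third reply is that Clopper-Pearson is conservative, with coverage of 97.6% to 99.1% in these rows, and that the 2.5-fold ratio is the most extreme row. The ratio does belong to the 0.01% row only. Wilson widths are nevertheless 2.64, 1.48 and 1.26 times the stated ones, so the gap does not come only from a conservative benchmark. In absolute terms the exact widths exceed the stated ones by 0.15, 0.10 and 0.08 percentage points.

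The reply also notes that each of the three half-widths already exceeds its rate, so an alert reader can see that precision is poor. That is true, but it does not tell the reader which rate can be excluded. Finally, the protocol's main adverse event summary is exposure-adjusted, and binomial widths of any kind describe only crude subject incidence. That limitation stands and also applies to the corrected table.

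**Conclusion.** The concern holds. The fault is the choice of method for rare events; the formula itself was evaluated correctly. In three of eight rows the stated figure is not the width of a 95% interval that 1600 subjects can deliver. Precision is overstated by factors of about 2.5, 1.4 and 1.25. From 1% upward exact widths are only 3% to 7% larger, and those rows can stand.

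The conclusion rests on three assumptions: that the Wald formula was used (inferred from the match in all eight rows), that subjects are independent, and that all 1600 contribute to crude incidence. The practical weight is moderate. The error affects what the plan claims about rare adverse events, but not the sample size or any planned analysis.

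**What to change.** Replace Table 5 in Protocol 10.2 and Table 3-1 in SAP 3.2 with Clopper-Pearson or Wilson widths, and name the method. For the 0.01%, 0.05% and 0.10% rows, add two items:

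- the upper bound when no event is seen: 0.23% two-sided, 0.19% one-sided;
- the probability of observing at least one subject with the event: 15%, 55% and 80%.

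State that the table refers to crude subject incidence. If any interval is later reported with crude adverse event incidences, use the same method. Leave N at 1600.

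The cost is one replaced table in each document, with no change to design, conduct or data collection. The stated precision for rare events becomes less favourable.
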